## 1. Research Background and Rationale

Postoperative nausea and vomiting (PONV) is a common complication following surgery. Reports indicate that the incidence of PONV is 30% among all postoperative patients and can reach up to 80% in high-risk patients. Well-established risk factors for increased PONV include female sex, age under 50 years, non-smoking status, and a history of PONV or motion sickness [1, 2]. PONV not only diminishes patients' well-being, but may also result in severe consequences such as dehydration, electrolyte imbalance, wound dehiscence, and regurgitation with aspiration. These complications can lead to delayed recovery, unplanned hospital admission, and postponed return to work. Such outcomes are associated with prolonged recovery room stay, delayed discharge, and increased healthcare costs [3-5]. Procedures such as laparoscopy, gynecological surgery, and operations of longer duration are also associated with an increased incidence of PONV. Similarly, the use of general anesthesia and postoperative administration of opioid drugs contribute to a higher incidence of this complication [6, 7].

It is well established that conventional opioid drugs increase the risk of PONV in a dose-dependent manner [8]. Although the exact mechanisms by which opioid drugs cause nausea and vomiting are not yet fully understood, multiple mechanisms may be involved [9]. At the cellular level, traditional opioid agonists bind to the MOR and stimulate G protein signaling to produce analgesia, while activation of the  $\beta$ -arrestin pathway leads to adverse effects related to respiratory and gastrointestinal function [10]. In preclinical studies,  $\beta$ -arrestin-2 gene knockout mice treated with morphine exhibited enhanced analgesic effects and reduced respiratory depression and gastrointestinal dysfunction compared with wild-type animals treated with morphine [11, 12].

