## **3. Research Protocol and Plan**

### **3.1 Study Design**

This study is a randomized, double-blind, parallel-controlled clinical trial to be conducted in the Department of Anesthesiology at the Second Xiangya Hospital of Central South University. Prior to initiation, the study will be approved by the hospital's medical ethics committee, and informed consent will be obtained from patients or their families. Patients will be randomized according to a computer-

generated randomization sequence into the sufentanil group and the oliceridine group. The sufentanil group will receive sufentanil for both anesthesia and postoperative analgesia, while the oliceridine group will receive oliceridine for both anesthesia and postoperative analgesia. Group allocation results are delivered to the anesthesia nurse using the sealed envelope method. Based on the study design and allocation, injection solutions with identical appearance and volume are prepared and provided to the attending anesthesiologist. The anesthesia nurse responsible for drug preparation does not participate in patient recruitment, randomization, data collection, or analysis.

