### 3.4 Outcome Measures and Follow-up Plan

Primary outcome measure: Incidence of PONV within 48 hours postoperatively. PONV will be assessed within 48 hours postoperatively in the ward by a blinded investigator. Subjects are required to use the simplified PONV impact scale to report whether any PONV events occurred in the past 48 hours and to provide a rating.

(Consisting of two questions: Q1. Have you experienced vomiting or symptoms of vomiting? If yes, how many episodes in total? Under what circumstances did it occur? Was any medication administered for treatment? Q2. Have you experienced nausea? If yes, did the sensation of nausea affect your daily activities? Was any medication administered for treatment?) Based on the number, frequency, and triggers of nausea and vomiting, the incidents are classified into four grades: absence of vomiting or nausea not requiring rescue treatment after onset is defined as complete remission; Mild PONV is defined as mild nausea or a single episode of vomiting

induced by drinking water or physical activity. Moderate PONV is defined as two episodes of vomiting or significant nausea requiring rescue therapy. Severe PONV is defined as more than two episodes of vomiting or the need for more than one dose of rescue therapy.

General patient data: including age, height, weight, BMI, ASA classification, smoking history, previous history of PONV, history of motion sickness, surgical history, history of hypertension, history of diabetes, among others.

Intraoperative indicators: surgical method, surgical site, blood loss, operative duration, anesthesia duration, anesthetic dosage, infusion volume, and incidence of hypotension.

Secondary outcome measures:

1) Record the occurrence of PONV separately for four time periods (T1: PACU stay; T2: from departure from PACU to 12 hours postoperatively; T3: 12 to 24 hours postoperatively; T4: 24 to 48 hours postoperatively). Incidence of postoperative vomiting (POV) and POV scores during the four time periods (T1–T4) within 48 hours after surgery. Record the use of rescue antiemetic medications.

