### 3.5 Statistical Analysis Plan

Sample size calculation: The primary outcome is the incidence of PONV within 48 hours postoperatively, and the sample size will be calculated based on this primary endpoint. According to the study by Zhao et al., the incidence of PONV within 48 hours after gynecological laparoscopic surgery is 71.7%. It is expected that the incidence of PONV will be reduced by at least 40%. Assuming  $\alpha = 0.05$  and a power of 80%, PASS 15 software was used to calculate a sample size of  $N = 45$  per group. Considering a 5% dropout rate, a total of 48 patients per group will be enrolled, requiring 96 subjects in total.

Statistical analysis was conducted using SPSS 26.0. Normally distributed continuous data were expressed as mean  $\pm$  standard deviation (mean  $\pm$  SD), and between-group comparisons were performed using the independent samples t-test. Non-normally distributed continuous data were expressed as median (M) and interquartile range (IQR), and between-group comparisons were performed using the Wilcoxon rank-sum test. Repeated measures data were analyzed using repeated measures analysis of variance or the generalized estimating equation model, according to the distribution characteristics of the data. Categorical data were expressed as rates or percentages, and comparisons were performed using the  $\chi^2$  test or Fisher's exact test. Ordinal data were analyzed using the rank-sum test. Subgroup analyses will be performed based on operative duration ( $\leq 2$ h or  $> 2$ h), smoking status (non-smoker or history of smoking within the past six months), history of chemotherapy, age ( $\leq 50$  or  $> 50$ ), and BMI (18-25 or 25-30), using logistic regression analysis. A P value  $< 0.05$  will be considered statistically significant.

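### Optional improvement: the primary PONV comparison appears to be unadjusted, although strong-candidate baseline predictors are named and collected; one prespecified two-covariate model would be cheap

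*Combined protocol and SAP*

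**What the plan says.** The outcome is binary: "Primary outcome measure: Incidence of PONV within 48 hours postoperatively" (section 3.4). Section 3.5 attaches no named test to it. The rule that covers it is the general one for categorical data: "Categorical data were expressed as rates or percentages, and comparisons were performed using the" chi-square or Fisher's exact test. Logistic regression appears only for subgroups: "Subgroup analyses will be performed based on operative duration", then "smoking status (non-smoker or history of smoking within the past six months), history of chemotherapy", age and BMI.

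Section 1 states: "Well-established risk factors for increased PONV include female sex, age under 50 years, non-smoking status, and a history of PONV or motion sickness". Section 3.4 collects age together with "smoking history, previous history of PONV, history of motion sickness". Section 3.1 describes a computer-"generated randomization sequence into the sufentanil group and the oliceridine group" and mentions no stratification factor. History of PONV or motion sickness therefore enters neither the allocation, nor a stated outcome model, nor a subgroup.

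**The concern.** The protocol itself identifies baseline factors that it regards as predictive and records them for every patient, yet the main comparison appears to ignore them. Adjusting for a baseline factor that truly predicts the outcome makes the treatment estimate more precise at the same sample size. It also removes the effect of any chance imbalance in that factor, which the allocation as described does not control. This trial has little margin: power is just under 80% at the 45 evaluable patients per arm it plans for.

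There is also a question of which result decides. No primary test is named, and logistic regression is already in the plan. An adjusted result could therefore be preferred, or set aside, after the data are seen.

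**Working it through.** **1. The plan's own figure.** Inputs from section 3.5: control rate 0.717; a 40% reduction, read as relative, giving 0.717 × 0.6 = 0.4302; alpha 0.05, taken as two-sided; power 80%. With the pooled two-proportion formula:

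- mean rate (0.717 + 0.4302)/2 = 0.5736; √(2 × 0.5736 × 0.4264) = 0.6994
- √(0.717 × 0.283 + 0.4302 × 0.5698) = √0.4480 = 0.6694
- n = [(1.960 × 0.6994 + 0.8416 × 0.6694)/0.2868]² = 45.5, so 46 per arm

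This agrees with the stated 45 to within one patient. (An absolute 40-point reduction would need only 24.) Dropout: 45/0.95 = 47.4, so 48. Power by the same formula is 79.6% at 45 per arm and 82.1% at 48. The unadjusted test therefore fits the sample size.

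**2. Assumptions for the adjusted analysis.** The documents give no prevalence or odds ratio (OR) for the predictors. Assumed: positive history of PONV or motion sickness in 40%; age 50 or under in 60%; ORs over the range shown. Marginal PONV rates are held at 71.7% and 43.0%.

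**3. Comparison.** Pearson chi-square against ordinary linear regression of PONV (0/1) on treatment, history and age group, with the treatment coefficient tested on t with N - 4 degrees of freedom. There were 80,000 simulated trials per scenario (Monte Carlo standard error of each power change about 0.1 point). Changes were taken before rounding.

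| ORs (history, age) | 48/arm: chi-square → linear | Change (points) | 45/arm: chi-square → linear | Change (points) | Mean 95% CI half-width at 48/arm, adjusted (unadjusted 19.2 points) |
|---|---|---|---|---|---|
| 1, 1 | 82.4% → 81.7% | -0.7 | 78.9% → 78.9% | 0.0 | 19.4 |
| 1.5, 1.5 | 82.2% → 82.1% | -0.1 | 78.8% → 79.7% | +0.8 | 19.2 |
| 2, 1.5 | 82.4% → 82.9% | +0.5 | 78.7% → 80.2% | +1.5 | 19.1 |
| 3, 2 | 82.5% → 84.6% | +2.2 | 78.9% → 82.2% | +3.3 | 18.6 |
| 3, 3 | 82.4% → 85.8% | +3.4 | 79.1% → 83.7% | +4.6 | 18.3 |

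Repeat simulations with other seeds agreed to within about 0.3 points.

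**4. How much is real precision.** At 48 per arm the standard deviation of the estimated risk difference goes from 0.0967 to 0.0977 (ORs 1, 1), 0.0965 to 0.0966 (1.5, 1.5), 0.0969 to 0.0938 (3, 2; -3.2%) and 0.0969 to 0.0924 (3, 3; -4.6%). At 45 per arm part of the power gain is not precision. Chi-square there rejects only 4.6–4.7% under the null. A size of 0.0463 corresponds to a critical value of 1.993 instead of 1.960, and (1.993 - 1.960) × normal density 0.288 ≈ 0.010, or about 1 point.

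**5. Validity.** With 57% PONV in both arms the linear model rejected in 4.8–5.1% of trials, and its interval coverage was 94.6–95.1%. A heteroskedasticity-robust standard error changed power by about 0.1 point. With arms of 48 and 43, null rejection was 5.0–5.3%.

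**6. Sensitivity to prevalence.** With history 20–60% and age 50 or under 50–80%, at 48 per arm, the change was -0.4 to 0.0 points at ORs 1.5, 1.5 and +1.3 to +2.4 points at 3, 2.

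**7. Chance imbalance.** At 48 per arm the probability that the arms differ by 15 points or more in history is 9.4%, 11.8% and 12.5% for prevalences of 30%, 40% and 50%. Such an imbalance shifts the raw risk difference by 1.2–1.5 points at OR 1.5 and 2.9–4.0 points at OR 3. The standard error of the raw difference is √(0.4480/48) = 0.097, or 9.7 points, so even the largest shift is 4.0/9.7 = 0.41 standard errors.

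**8. Disagreement between the analyses.** In scenario order, the linear model and chi-square differ on significance in 2.4%, 3.5%, 4.1%, 6.2% and 7.3% of trials at 48 per arm, and in 3.0%, 3.9%, 5.0%, 7.2% and 8.4% at 45.

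**The case against.** The strongest reply is that nothing is broken. The unadjusted test is valid in a randomised trial, matches the sample-size calculation and is easy to explain. The benefit depends on predictor strengths that the documents do not give. With weak predictors there is no gain at 48 per arm, and in the favourable case of ORs 3 and 2 the interval half-width falls only from 19.2 to 18.6 points. The details of the model are also choices: linear rather than logistic regression, age cut at 50, two histories merged into one, smoking left out. Naming chi-square as the primary test would equally prevent a choice made after the data are seen.

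Most of this stands, and it is why the point is optional. It does not remove the point. The likely loss is under 1 point of power, and at the planned 45 evaluable per arm the adjusted model did not fall materially below chi-square. There is a specific reason to prefer the linear form. A logistic likelihood-ratio test with two binary covariates rejected 5.3–6.0% under the null at 45 per arm, although those runs used 71.7% in both arms, where chi-square itself rejected 5.1–5.5%. The linear coefficient is also directly a risk difference, the scale on which the trial was sized. Disagreement of up to about 8% at 45 per arm is an argument for fixing the deciding analysis in advance, whichever it is.

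**Conclusion.** The point holds as an optional improvement of modest and conditional value. If history and age group predict PONV strongly (ORs of about 3 and 2 or more), adjustment adds about 2 to 3.5 points of power at 48 per arm and narrows the interval by 0.6 to 0.9 points on each side. At 45 per arm it adds 3.3 to 4.6 points, about 1 of which is a test-size effect. If they predict weakly (about 1.5 or less), there is no real gain at 48 per arm and possibly a loss of up to about 1 point. These figures rest on the relative reading of the 40% reduction and on assumed prevalences and ORs. The benefit of fixing the deciding analysis before unblinding does not depend on predictor strength. Confidence is medium, because the documents do not show which scenario applies.

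**What to change.** Before unblinding, add one paragraph to section 3.5:

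- **Primary analysis:** ordinary linear regression of PONV within 48 hours (0/1) on treatment, history of PONV or motion sickness (yes/no) and age (≤50, >50, the cut already used for subgroups).
- **Reporting:** take the adjusted risk difference, its 95% CI and the P value all from the treatment coefficient, on t with N - 4 degrees of freedom.
- **Decision rule:** only this model decides significance; the chi-square test is supportive.
- **Not covariates:** operative duration, which section 3.4 lists under "Intraoperative indicators: surgical method, surgical site, blood loss, operative duration, anesthesia duration" and which is known only after randomisation; and smoking, which can stay in the subgroup list because the documents give no smoking rate to support a third covariate. Female sex cannot discriminate in a gynaecological population.

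The cost is this paragraph; no new data are needed. The downsides are a loss of up to about 1 point of power at 48 per arm if the factors turn out to be weak, and occasional disagreement with chi-square, which the decision rule settles. Keeping the unadjusted test is also legitimate; in that case name it explicitly as the primary test.

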Postoperative analgesia assessment: Resting visual analog scale (VAS) pain scores at four time points (T1–T4) within 48 hours after surgery, measured using a 10 cm movable ruler with a numerical scale of 0–10 on the reverse side. The left end (“0”) indicates no pain, while the right end (“10”) represents unbearable severe pain. Record the number of PCA presses, total analgesic consumption, and the use of rescue analgesics within 48 hours after surgery.

Ramsay sedation score at 2 hours postoperatively: a score of 1 indicates agitation, 3 or 4 indicates somnolence, and 5 or 6 indicates excessive sedation.

Sleep quality score on the night after surgery: Patient sleep quality will be assessed using a numerical rating scale based on an 11-point Likert scale, ranging from 0 to 10. A score of 0 indicates complete insomnia and extremely poor sleep quality, while a score of 10 represents excellent sleep quality. Severe insomnia is defined as a score of 0–3, moderate insomnia as 4–6, and good sleep quality as 7–10.

QOR-15 score: A score of 0 indicates extremely poor quality of recovery, while a score of 150 indicates excellent quality of recovery. Assessments will be conducted preoperatively, on postoperative day 1, and on postoperative day 3.

Length of stay in the recovery room, time to first postoperative bowel movement, time to resumption of oral intake, time to first postoperative feeding, time to first

postoperative ambulation, and any other adverse events.

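### Section 3.5 applies one P < 0.05 rule to about 17 to 30 secondary comparisons, with no ranking, error control or exploratory label

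*Combined protocol and SAP*

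**What the plan says.** Section 3.5 names one primary outcome ("The primary outcome is the incidence of PONV within 48 hours postoperatively") and bases the sample size on it alone. It then assigns tests by type of data, lists five subgroup factors, and closes with a single threshold: P below 0.05 "will be considered statistically significant". The threshold is not limited to the primary outcome.

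Section 3.4 lists the secondary outcomes. The first item begins "Record the occurrence of PONV separately for four time periods" and adds vomiting incidence and vomiting score over the same periods, then rescue antiemetic use. Resting pain at T1 to T4, PCA and analgesic use, sedation, sleep and QoR-15 follow. The list ends with recovery-time measures, including "time to first postoperative bowel movement, time to resumption of oral intake", and other adverse events. No outcome is placed above another, none is called key or exploratory, and no multiplicity procedure appears in either section.

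Section 3.5 also says that repeated-measures data go to repeated measures ANOVA or a GEE model. It does not say whether the T1 to T4 outcomes then get one overall test, a test per period, or both.

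**The concern.** A threshold of 0.05 limits the error rate of one test. Applied to a long list, with every result below it eligible to be called significant, it leaves the chance of at least one false claim across the list uncontrolled. The unstated number of tests adds to this, because the choice between an overall test and period-by-period tests could be made after the data are seen.

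What is at stake is the interpretation of the secondary results. If the primary comparison is null, nothing in the plan stops an isolated P < 0.05 on pain, PCA use, QoR-15 or a recovery time from being reported as a demonstrated benefit. The benefit statements in section 5 mention pain control, analgesia and recovery quality, so such a result would find a ready use.

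**Working it through.** **1. The plan's own figure.** The plan states no family-wise error rate. Its only related figure is the sample size. Inputs from section 3.5: a control-group rate of 71.7%, taken there from a cited study; a fall in that rate by 40% or more; two-sided alpha 0.05 (sidedness is an assumption, as it is not stated); power 80%.

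- Reading the reduction as relative, p2 = 0.717 × 0.6 = 0.4302.
- The pooled formula, with mean rate 0.5736, is n = [1.960 × √(2 × 0.5736 × 0.4264) + 0.842 × √(0.717 × 0.283 + 0.4302 × 0.5698)]² / 0.2868² = 45.5.
- This agrees with the stated 45 to within rounding. Dropout: 45 / 0.95 = 47.4, so 48 per group, as the plan has it ("a total of 48 patients per group will be enrolled, requiring 96 subjects in total").

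The size is therefore set for one comparison at 0.05, the primary one.

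**2. Count of secondary comparisons (section 3.4).**

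| Outcome | Each time point tested | One test per repeated outcome |
|---|---|---|
| PONV, T1–T4 | 4 | 1 |
| Vomiting incidence, T1–T4 | 4 | 1 |
| Vomiting score, T1–T4 | 4 | 1 |
| Rescue antiemetics | 1 | 1 |
| Resting VAS, T1–T4 | 4 | 1 |
| PCA presses, consumption, rescue analgesics | 3 | 3 |
| Ramsay score | 1 | 1 |
| Sleep score | 1 | 1 |
| QoR-15, days 1 and 3 | 2 | 1 |
| Five recovery times | 5 | 5 |
| Other adverse events (at least) | 1 | 1 |
| **Total** | **30** | **17** |

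The five subgroup factors are left out of this count.

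**3. Chance of at least one P < 0.05 when no secondary effect exists.** For k independent tests it is 1 − 0.95^k:

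- k = 30: 1 − 0.95^30 = 0.785, with 30 × 0.05 = 1.5 false positives expected.
- k = 17: 1 − 0.95^17 = 0.582, with 17 × 0.05 = 0.85 expected.

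The documents give no correlations between outcomes, so the values below are assumptions. They use jointly normal two-sided test statistics with the same correlation between every pair.

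| Assumed correlation | 30 tests | 17 tests |
|---|---|---|
| 0 | 79% | 58% |
| 0.3 | 66% | 49% |
| 0.5 | 51% | 39% |
| 0.8 | 26% | 21% |

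If correlation is instead set at 0.3 to 0.8 within a domain (emesis, analgesia, recovery and so on) and 0 to 0.3 between domains, the chance runs from about 74% down to 48% for 30 tests, and from 56% down to 40% for 17.

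**4. Direction.** With two-sided tests and no true effect, half the false positives favour each drug. Expected false benefits for oliceridine are 30 × 0.025 = 0.75, or 17 × 0.025 = 0.43. The chance of at least one false benefit is:

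- 30 tests: 1 − 0.975^30 = 53% if independent, 35% at correlation 0.3, 26% at 0.5.
- 17 tests: 1 − 0.975^17 = 35% if independent, 25% at correlation 0.3, 19% at 0.5.

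**The case against.** The strongest reply is that the problem is smaller than a count of 30 suggests, and confined to secondary results. Several parts of it stand.

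- **The count.** Section 3.5 assigns repeated data to repeated measures ANOVA or GEE, so 17 is a fair reading. But the plan does not exclude period-by-period tests, and section 3.4 asks for PONV to be recorded by period, so 30 is fair too.
- **Overlap.** Independence is a poor model here. PONV, vomiting incidence, vomiting score and rescue antiemetic use overlap by definition. With a fixed bolus and no background infusion (section 3.3), PCA presses and consumption move together. Resumption of oral intake and first feeding look close to the same event. The 58% and 79% figures are therefore best treated as upper ends for their counts.
- **The null scenario.** The calculation assumes no true secondary effect. Real effects on some outcomes, or conservative Fisher tests on rare events, would lower the figures.
- **The primary outcome.** There is one primary outcome and no interim analysis is described, so its error rate is not inflated by this gap.

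A reader might infer that a false-positive secondary finding is more likely than not. The documents do not support that as a general statement: with 17 tests and an assumed correlation of 0.3 or 0.5 the chance is below half. A reader might also expect one or two false benefits for oliceridine. The 1.5 expected false positives in the 30-test case fall in both directions, so that figure would be about twice too high. Nor does section 5 show that a false secondary result would determine the trial's conclusion. It is prospective benefit text rather than a rule for drawing conclusions, and patient satisfaction, which it mentions, is not among the outcomes in section 3.4.

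None of this supplies the missing ranking, correction or label.

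**Conclusion.** The concern holds in this form. The plan applies one unadjusted threshold to about 17 to 30 secondary comparisons and says nothing about which of them may support a claim. If no secondary effect exists, the chance of at least one P < 0.05 is 58% to 79% under independence and about 39% to 66% at an assumed equal correlation of 0.3 to 0.5, with 0.4 to 0.75 false positives expected in favour of oliceridine. Whether the chance exceeds one half depends on the number of tests and their correlation, and the plan gives neither. The case for a change does not rest on passing one half: even at an assumed correlation of 0.8 throughout, the chance is 21% to 26%, well above 5%.

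This should be corrected because it governs how secondary results may be described. It does not threaten the primary analysis.

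**What to change.** Amend section 3.5 along these lines: *Only the incidence of PONV within 48 hours is confirmatory, tested at two-sided 0.05. All secondary outcomes are exploratory and are reported as estimates with 95% confidence intervals, without claims of statistical significance.* State in the same place whether each T1 to T4 outcome and QoR-15 is summarised by one repeated-measures analysis, by period, or both.

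If the sponsor wants some secondary claims, it can name a short set of key secondary outcomes before unblinding and test them with Holm's correction only if the primary result is significant. Which outcomes to name is the sponsor's choice. Correcting the whole list is possible but severe: the first Holm step would need P below 0.05 / 30 = 0.0017, or 0.05 / 17 = 0.0029.

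The cost is a few lines of wording, with no new data or patients. The downside is that fewer secondary results can be called significant.
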